Baseline DENV and ZIKV serostatus will be determined via IgM antibody and IgG ELISA assays, with subject results reported as either 'positive' or 'negative'. If a subject has a positive ZIKV result from either the IgM or IgG ELISA assays, they will be considered ZIKV seropositive at baseline. If a subject has inconclusive results for their baseline flavivirus immune status, they will not be included in analyses stratified by baseline flavivirus immune status but will be included in analyses of all subjects.

Post-Baseline Seropositivity

Seropositivity post-baseline is defined as a titer ≥ 10 and ≥ 100 for ZIKV MN50 and a titer ≥ 200 and ≥ 600 for ZIKV ELISA.

Seroconversion

Seroconversion for ZIKV MN50 titers and ZIKV ELISA titers is defined as ≥ 4 -fold rise from baseline.

Acute Febrile Illness and Acute Rash Illness

Acute febrile illness (AFI) is defined as grade 1 or higher fever on at least 2 consecutive days accompanied by any of the following: new rash not limited to vaccination site, arthralgia, or nonpurulent conjunctivitis. Acute rash illness (ARI) is defined as any new rash not limited to vaccination site.

Laboratory Confirmation of ZIKV or DENV Infection Among Those with AFI or ARI

Among subjects with AFI or ARI, laboratory confirmation of ZIKV or DENV infection will be made by either 1) evidence of acute ZIKV and DENV infection within 14 days of symptom onset (confirmed via PCR) or 2) a 4-fold rise in DENV or ZIKV neutralization titers between samples collected at the last visit prior to and at the first visit following the AFI/ARI illness visit, where available.

Consideration of ZIKV Microneutralization Assay Results in Analysis

The lower limit of quantitation (LLOQ) for ZIKV microneutralization assay results is 10. Any values less than the LLOQ will be assigned a value of 5 by the lab. This imputed value will be used for the purpose of calculating summary statistics such GMT and will be displayed in listings of immunogenicity data. If a subject has a baseline titer below the LLOQ (reported as 5), then they will be considered seroconverted if the post-baseline titer is at least 20 (at least a 4-fold rise). Similarly, a subject with a baseline ZIKV MN50 below the LLOQ will be considered seropositive if the post-baseline titer is at least 10 or 100, as applicable.

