4.5. Immunogenicity and Safety Variables

In general, multiple observations within a specific visit period were accepted. In the case of multiple observations within a specific window, the assessment value closest to the scheduled visit date will be used in the analyses for the post-baseline records. If observations have the same distance to the scheduled assessment, the latest one will be used. Unless otherwise specified, the last assessment value recorded prior to the prime dose will be used as baseline. All the recorded data will be listed. Samples from days on which a subject was vaccinated were collected prior to vaccination.

All subjects were to have venous blood samples for assessment of humoral immunity collected on Days 1, 15, 29, 43, 57, 209, 388, and 569. Assay results are reported as the ZIKV titers giving 50% reduction in viral infection (MN50) and IgG ELISA titers. DENV neutralization titers were also to be recorded in subjects reporting ARI or AFI. Samples from the immunogenicity visits immediately before and after the illness visit were used to measure DENV titers, which will be used to aid laboratory confirmation of ZIKV/DENV infection.

Solicited adverse events were collected from the time of study vaccine administration through Day 8 after each dose. Subjects received a memory aid to record any solicited AEs on each day. The following injection site reactogenicity events were measured and grading according to the scale in [Table 3](#) and [Table 4](#): pain, tenderness, pruritis, ecchymosis, erythema, and induration. The following systemic solicited events were measured and graded according to the scale in [Table 4](#) and [Table 5](#): feverishness, fatigue, malaise, myalgia, arthralgia, headache, nausea, vomiting, diarrhea, abdominal pain, rash, and fever.

Vital signs of heart rate and blood pressure were measured in subjects at Days 1, 2, 8, 15, 29, 30, 36, 43, and 57. The measurements were assessed for adverse events of bradycardia/tachycardia and systolic and diastolic hypotension/hypertension according to the scale in [Table 6](#).

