Table 142: Summary of AFI/ARI Events Reported Through 12 Months Post Final Vaccination by Treatment Group – Baseline ZIKV Seronegative Subjects**Table 143: Summary of AFI/ARI Events Reported Through 12 Months Post Final Vaccination by Treatment Group – Baseline ZIKV Seropositive and DENV Seropositive Subjects****Table 144: Summary of AFI/ARI Events Reported Through 12 Months Post Final Vaccination by Treatment Group – Baseline ZIKV Seropositive and DENV Seronegative Subjects****Table 145: Summary of AFI/ARI Events Reported Through 12 Months Post Final Vaccination by Treatment Group – Baseline ZIKV Seronegative and DENV Seropositive Subjects**

Table 146: Summary of AFI/ARI Events Reported Through 12 Months Post Final Vaccination by Treatment Group – Baseline ZIKV Seronegative and DENV Seronegative Subjects

Table 147: Number of Laboratory Confirmed ZIKV or DENV Infections Overall and by Confirmation Method – All Subjects

[Implementation note: This table can include any subjects who did not have a baseline flavivirus status observed.]

Infection Confirmation Status	2.5 mcg ZPIV (N=X)				5 mcg ZPIV (N=X)				Placebo (N=X)				All Subjects (N=X)			
	Number of Events	Number of Subjects	% of Subjects	95% CI	Number of Events	Number of Subjects	% of Subjects	95% CI	Number of Events	Number of Subjects	% of Subjects	95% CI	Number of Events	Number of Subjects	% of Subjects	95% CI
Positive by PCR ^a	X	X	XX	X.X, X.X	X	X	XX	X.X, X.X	X	X	XX	X.X, X.X	X	X	XX	X.X, X.X
Positive by 4-Fold Titer Rise ^b																
Any Positive Confirmation ^{a,b}																
Negative Lab Confirmation																

N = Number of subjects in the Safety Population

% = percentage of subjects reporting at least one AFI/ARI event/total number of subjects in the Safety population in the group

95% CI is calculated using the Clopper-Pearson methodology for a binomial distribution.

This table includes subjects who only received dose 1.

^a PCR confirmation includes a positive PCR result for at least one of ZIKV (blood or urine) or DENV.^b 4-fold rise in either ZIKV or DENV neutralization titers after the ARI/AFI illness visit compared to before the illness visit.^c Includes hospitalization or other medical care

Tables with similar format:

Table 148: Number of Laboratory Confirmed ZIKV or DENV Infections Overall and by Confirmation Method – Baseline ZIKV Seropositive Subjects

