Nonpurulent conjunctivitis																
Headache																
Respiratory distress																
Retro-orbital pain																
Myalgia/Muscle pain																
Arthralgia/Joint pain																
Arthritis																
Nausea																
Abdominal pain																
Vomiting*																
Persistent vomiting*																
Bleeding*																

Table 161: Maximum Severity of Symptoms of AFI/ARI Events Reported Through 12 Months Post Final Vaccination by Treatment Group – All Subjects

Symptom	2.5 mcg ZPIV (N=X)				5 mcg ZPIV (N=X)				Placebo (N=X)				All Subjects (N=X)			
	None	Mild	Moderate	Severe	None	Mild	Moderate	Severe	None	Mild	Moderate	Severe	None	Mild	Moderate	Severe
	n (%)	n (%)	n (%)	n (%)	n (%)	n (%)	n (%)	n (%)	n (%)	n (%)	n (%)	n (%)	n (%)	n (%)	n (%)	n (%)
N = number of subjects reporting at least one AFI/ARI n=number of subjects reporting the symptom % =percentage of subjects reporting the symptom out of the total number of subjects reporting at least one AFI/ARI If multiple AFI/ARI are reported for a subject, then the maximum severity is considered for each symptom. This table includes subjects who only received dose 1. * Reported as None/Any																

Tables with similar format:

Table 162: Maximum Severity of Symptoms of AFI/ARI Events Reported Through 12 Months Post Final Vaccination by Treatment Group – Baseline ZIKV Seropositive Subjects**Table 163: Maximum Severity of Symptoms of AFI/ARI Events Reported Through 12 Months Post Final Vaccination by Treatment Group – Baseline ZIKV Seronegative Subjects****Table 164: Maximum Severity of Symptoms of AFI/ARI Events Reported Through 12 Months Post Final Vaccination by Treatment Group – Baseline ZIKV Seropositive and DENV Seropositive Subjects****Table 165: Maximum Severity of Symptoms of AFI/ARI Events Reported Through 12 Months Post Final Vaccination by Treatment Group – Baseline ZIKV Seropositive and DENV Seronegative Subjects****Table 166: Maximum Severity of Symptoms of AFI/ARI Events Reported Through 12 Months Post Final Vaccination by Treatment Group – Baseline ZIKV Seronegative and DENV Seropositive Subjects****Table 167: Maximum Severity of Symptoms of AFI/ARI Events Reported Through 12 Months Post Final Vaccination by Treatment Group – Baseline ZIKV Seronegative and DENV Seronegative Subjects**

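### One 4-fold titre rise between two scheduled sera confirms every AFI/ARI illness visit in that gap, so the event count of confirmed infections can exceed the number of infections

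*SAP*

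**What the plan says.** SAP 3.3 gives two routes to laboratory confirmation among subjects with AFI or ARI: PCR evidence within 14 days of onset, or "a 4-fold rise in DENV or ZIKV neutralization titers between samples collected at the last visit prior to and at the first visit following" the illness visit, where available. SAP 4.5 identifies the sera: "Samples from the immunogenicity visits immediately before and after the illness visit were used to measure DENV titers". Its schedule lists samples "collected on Days 1, 15, 29, 43, 57, 209, 388, and 569"; Protocol 8.4.1 and SAP Table 14 add Day 750.

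Tables 147-153 are titled "Number of Laboratory Confirmed ZIKV or DENV Infections Overall and by Confirmation Method". Their columns are *Number of Events*, *Number of Subjects*, *% of Subjects* and a 95% CI. Their rows are PCR positive, titre positive, any positive, and negative. Footnote b gives the titre criterion as a "4-fold rise in either ZIKV or DENV neutralization titers after the ARI/AFI illness visit compared to before the illness visit". Tables 154-160 use the same footnote with AFI/ARI events as the denominator.

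The SAP expects repeat illnesses. The Table 161 footnote says: "If multiple AFI/ARI are reported for a subject, then the maximum severity is considered for each symptom". Table 168 repeats that rule, and Tables 175 and 182 add a maximum rule for duration. No passage says how many infections one titre rise may stand for when several illnesses fall between the same two sera.

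**The concern.** Exploratory endpoint 2 (SAP 3.2) is the number and severity of laboratory-confirmed ZIKV and DENV infections. A rise between two scheduled sera shows that an infection occurred somewhere in the gap. It does not show which illness in the gap it caused, or that there was more than one infection. The rule is nevertheless applied separately to each illness.

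ARI is any new rash beyond the vaccination site, so an unrelated rash qualifies easily. Each long gap also contains two phone visits that ask about AFI/ARI (Protocol 8.3.7 to 8.3.17). More than one illness in a gap is therefore plausible. If one of them is a real infection, the others inherit its confirmation.

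**Working it through.** The plan states no figure for this point, so there is none to reproduce. The check applies the rule as written and then sizes the effect.

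**1. Gaps between sera** (days from SAP 4.5 and Protocol 8.4.1; windows from Protocol Table 2)

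| Pair of sera | Nominal gap, days | Range with windows |
|---|---|---|
| Day 57 to 209 | 209 − 57 = 152 | 135 to 169 |
| Day 209 to 388 | 388 − 209 = 179 | 151 to 207 |
| Day 388 to 569 | 569 − 388 = 181 | 153 to 209 |
| Day 569 to 750 | 750 − 569 = 181 | 153 to 209 |

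Up to Day 57 the nominal gap is 14 days. The long gaps make up 152 + 179 + 181 + 181 = 693 of the 749 days from Day 1 to Day 750, or 92.5%. That share applies to Tables 147-153, whose titles set no time limit. Tables 154-188 are titled through 12 months after the final vaccination, about Day 388, so only the first two long gaps matter there: (388 − 57)/(388 − 1) = 331/387 = 85.5%.

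**2. The rule as written.** Let k illness visits fall in one gap, with one 4-fold rise across it. Each visit has the same last serum before and first serum after, so each meets footnote b: k = 2 gives 2 confirmed events in 1 subject, and k = 3 gives 3 in 1 subject. If one of two illnesses is PCR positive and the other PCR negative, the second still enters the titre-positive and any-positive rows and leaves the negative row.

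**3. Effect by table**

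- Tables 147-153: *Number of Events* is too high. *Number of Subjects* and *% of Subjects* are unchanged, because a subject counts once.
- Tables 154-160: event counts, percentages and intervals shift, including the medication and medical-treatment rows. Illustration with 10 events, two sharing a gap and one of those PCR positive: as written, 2/10 = 20% (Clopper-Pearson 95% CI 2.5% to 55.6%); with one event confirmed, 1/10 = 10% (0.3% to 44.5%).
- Tables 168-174 and 182-188: these count subjects and keep the maximum severity or duration. Infections are not counted twice. Symptoms of an unrelated illness can be filed under a confirmed status, and under the maximum rule they can only add to or raise that subject's values.

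**4. Size.** The documents give no AFI/ARI rate, so a rate λ per person-year is assumed. Extra counts per titre-confirmed infection in a gap of G days = λ × G/365.25. With G = 180:

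- λ = 0.1: 0.1 × 180/365.25 = 0.049
- λ = 0.2: 0.099
- λ = 0.5: 0.246

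For the whole trial, take Poisson illnesses, 90 subjects with complete follow-up, one 152-day gap and three of 181 days (the 179-day gap rounded up). With m = λ × G/365.25, the chance of two or more illnesses in a gap is 1 − e^(−m)(1 + m). Summed over all gaps, the expected number of subject-gaps with two or more illnesses is 0.4 at λ = 0.1, 2.4 at λ = 0.25 and 8.7 at λ = 0.5. These are counts before a 4-fold rise is required, so fewer would produce an over-count.

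**The case against.** The best defence is that Table 147 counts AFI/ARI events, not infections: the column is headed that way, and a negative row cannot be a count of infections. Listing 12 shows PCR results and the day pair behind each rise, so a reader could spot two illnesses resting on one pair. The endpoint is exploratory and descriptive, with no test planned on these counts. This limits the consequence. It does not settle the matter, because the table title calls the quantity infections, SAP 9.9 promises a total of laboratory-confirmed infections, and no other shell supplies one.

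Three stronger readings are tempting, and the documents do not support them.

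- *One rise will be reported as several infections.* This is conditional. It needs two or more illness visits in the same gap, a 4-fold rise, and both sera available. Illnesses that began more than 14 days before being reported get a history only (Protocol 7.1.3).
- *Unrelated rashes dilute the severity of true infections.* In Tables 168-174 and 182-188 the true and the unrelated illness belong to the same subject and the maximum is kept, so a mild rash cannot lower the recorded value. Only the event-based medication and medical-treatment rows of Tables 154-160 could be diluted.
- *The share of subjects infected is inflated.* It is not; see step 3 of the working.

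A cap of one infection per pair of sera, regardless of virus, would also be wrong. Footnote b pools ZIKV and DENV, and separate rises to each in one gap can be two infections.

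**Conclusion.** The point holds as a conditional fault in a stated counting rule. The attribution error is certain whenever illnesses share a pair of sera that shows a rise and not all of them were caused by the infection behind it. How often that happens is unknown. The sizing rests on assumed illness rates, a Poisson model and complete follow-up; at low rates the over-count may be nil. Confirmed infections may be few in arms of about 45, 35 and 10 subjects, so even one false count could be visible. The rule should be added before the final tables are produced, so that the choice is not left to programming.

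**What to change.** In SAP 3.3 and footnote b, state that a 4-fold rise to a given virus between one pair of consecutive immunogenicity sera confirms at most one infection per subject and virus. Then:

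- If an illness in the gap is PCR positive for that same virus, attribute the rise to it and do not use the rise to confirm any other illness.
- If none is, and two or more illnesses share the pair, count one infection in Tables 147-153. Show those illnesses in a separate row, *titre rise, illness not attributable*, in Tables 154-160, 168-174 and 182-188, with severity and duration still reported.
- A single illness in the gap is handled as now.

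Two housekeeping items go with this. SAP 9.9 assigns the infection total to Tables 154-158 while the shell title sits on Tables 147-153, so these should be aligned. Protocol 3.2.3 carries the same illness-level criterion, so the added rule should be recorded in SAP Section 15.

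The cost is one derivation rule and one extra row in the shells. No new data are needed, since Listing 12 already holds the day pairs and the PCR result by virus. The small downside is that a true second infection with the same virus in one gap, without PCR, would be counted once.

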9.9. Other Safety Measures

Summary tables of acute febrile illness (AFI) and acute rash illness (ARI) events will be presented. The percentage of subjects who develop ARI or AFI will be summarized by treatment group and baseline flavivirus status. Additionally, summary tables for AFI/ARI events will be presented by baseline flavivirus status.

Summaries of subjects reporting any events, any medically treated events, and any events requiring concomitant medication, including the total number of events and the number, percentage and exact 95% Clopper-Pearson CI of subjects reporting an event, will be presented for all subjects and by baseline flavivirus immune status in [Table 140](#), [Table 141](#), [Table 142](#), [Table 143](#), and [Table 144](#). Similar summaries presented by infection confirmation method are presented in [Table 147](#), [Table 148](#), [Table 149](#), [Table 150](#) and [Table 151](#).

Summaries of laboratory confirmed ZIKV and DENV infections are also presented. ZIKV and DENV infection is presented via two methods: subjects presenting with ARI/AFI and positive Arbovirus PCR result within 14 days of symptom onset or subjects presenting with ARI/AFI and a 4-fold rise in ZIKV or DENV titers following the onset of illness compared to prior to illness. The total number of laboratory confirmed ZIKV or DENV infections are summarized by treatment group, baseline flavivirus status, and confirmation method in [Table 154](#), [Table 155](#), [Table 156](#), [Table 157](#), and [Table 158](#).

The distribution of the maximum severity of symptoms of each ARI/AFI event by baseline flavivirus status and treatment group will be presented in [Table 161](#), [Table 162](#), [Table 163](#), [Table 164](#), and [Table 165](#), as well as by infection confirmation status in [Table 168](#), [Table 169](#), [Table 170](#), [Table 171](#), and [Table 172](#). For subjects reporting at least one AFI/ARI the duration of reported symptoms will be described in [Table 175](#), [Table 176](#), [Table 177](#), [Table 178](#), [Table 179](#), and by infection confirmation status in [Table 182](#), [Table 183](#), [Table 184](#), [Table 185](#), and [Table 186](#).

Individual subject listings of AFI/ARI data will be included in [Listing 12](#) (subject information), [Listing 13](#) (medical treatment sought for ARI/AI), [Listing 14](#) (ARI/AI symptoms), [Listing 15](#) (vital signs), and [Listing 16](#) (laboratory results).

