Table 138: Number and Percentage of Subjects Reporting Serious Adverse Events Related to Study Treatment by MedDRA System Organ Class, Preferred Term, Treatment Group, and Baseline Flavivirus Immune Status

Table with similar format to Table 111:

Table 139: Duration (Days) of Serious Adverse Events Related to Study Treatment by MedDRA System Organ Class, Preferred Term, Treatment Group, and Baseline Flavivirus Immune Status

Table 140: Summary of AFI/ARI Events Reported Through 12 Months Post Final Vaccination by Treatment Group – All Subjects

[Implementation note: This table can include any subjects who did not have a baseline flavivirus status observed.]

Infection Confirmation Status	2.5 mcg ZPIV (N=X)				5 mcg ZPIV (N=X)				Placebo (N=X)				All Subjects (N=X)			
	Number of Events	Number of Subjects	% of Subjects	95% CI	Number of Events	Number of Subjects	% of Subjects	95% CI	Number of Events	Number of Subjects	% of Subjects	95% CI	Number of Events	Number of Subjects	% of Subjects	95% CI
All Events	x	x	xx	x.x, x.x	x	x	xx	x.x, x.x	x	x	xx	x.x, x.x	x	x	xx	x.x, x.x
Events Requiring Concomitant Medication																
Events Requiring Medical Treatment ^a																

N = Number of subjects in the Safety population
% = percentage of subjects reporting at least one AFI/ARI event out of total number of subjects in the Safety population in the group
95% CI is calculated using the Clopper-Pearson methodology for a binomial distribution.
This table includes subjects who only received dose 1.
^aIncludes hospitalization or other medical care

Tables with similar format:

Table 141: Summary of AFI/ARI Events Reported Through 12 Months Post Final Vaccination by Treatment Group – Baseline ZIKV Seropositive Subjects

[Implementation note: If no subjects are flavivirus positive at baseline, replace this table with the following note: 'Table not generated since no positive arbovirus results were reported for ZIKV or DENV.]

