Table 149: Number of Laboratory Confirmed ZIKV or DENV Infections Overall and by Confirmation Method – Baseline ZIKV Seronegative Subjects

Table 150: Number of Laboratory Confirmed ZIKV or DENV Infections Overall and by Confirmation Method – Baseline ZIKV Seropositive and DENV Seropositive Subjects

Table 151: Number of Laboratory Confirmed ZIKV or DENV Infections Overall and by Confirmation Method – Baseline ZIKV Seropositive and DENV Seronegative Subjects

Table 152: Number of Laboratory Confirmed ZIKV or DENV Infections Overall and by Confirmation Method – Baseline ZIKV Seronegative and DENV Seropositive Subjects

Table 153: Number of Laboratory Confirmed ZIKV or DENV Infections Overall and by Confirmation Method – Baseline ZIKV Seronegative and DENV Seronegative Subjects

Table 154: Summary of ARI/AI Events Occurring Through 12 Months Post Final Vaccination by ZIKV or DENV Infection Status and Confirmation Method – All Subjects

[Implementation note: This table can include any subjects who did not have a baseline flavivirus status observed.]

Infection Confirmation Status	2.5 mcg ZPIV (N*=X)				5 mcg ZPIV (N*=X)				Placebo (N*=X)				All Subjects (N*=X)			
	Number of Subjects	Number of Events	% of Events	95% CI	Number of Subjects	Number of Events	% of Events	95% CI	Number of Subjects	Number of Events	% of Events	95% CI	Number of Subjects	Number of Events	% of Events	95% CI
All Events																
Positive by PCR ^a	X	X	XX	X.X, X.X	X	X	XX	X.X, X.X	X	X	XX	X.X, X.X	X	X	XX	X.X, X.X
Positive by 4-Fold Titer Rise ^b																
Any Positive Confirmation ^{a,b}																
Negative Lab Confirmation																
Events Requiring Concomitant Medication																
Positive by PCR ^a																
Positive by 4-Fold Titer Rise ^b																
Any Positive Confirmation ^{a,b}																
Negative Lab Confirmation																
Events Requiring Medical Treatment ^c																
Positive by PCR ^a																
Positive by 4-Fold Titer Rise ^b																
Any Positive Confirmation ^{a,b}																
Negative Lab Confirmation																

N* = Total number of AFI/AI events

% = number of AFI/AI events / total number of AFI/AI events (N*)

95% CI is calculated using the Clopper-Pearson methodology for a binomial distribution.

This table includes subjects who only received dose 1.

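### Tables 154–160 put exact binomial 95% intervals on illness events with no allowance for repeat illnesses in one subject, so the 95% level is not assured

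*SAP*

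**What the plan says.** The footnotes to the Table 154 shell (SAP Appendix 1) define the denominator as "N* = Total number of AFI/AI events", where AFI/AI evidently means AFI/ARI. The percentage is "number of AFI/AI events / total number of AFI/AI events (N"*), and "95% CI is calculated using the Clopper-Pearson methodology for a binomial distribution". Tables 155–160 use the same format for the baseline serostatus subgroups. No footnote restricts a subject to one event or adjusts for clustering.

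The neighbouring shells use a different unit. Table 140 reports the "percentage of subjects reporting at least one AFI/ARI event out of total number of subjects in the Safety population in the group", and Table 147 has an almost identical footnote. Both carry Clopper-Pearson intervals on subjects.

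The Table 161 shell provides for repeats: "If multiple AFI/ARI are reported for a subject, then the maximum severity is considered for each symptom". The duration shells (Tables 175 and 182) collapse repeats in a similar way.

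Section 9.9 describes the Table 140 family as "including the total number of events and the number, percentage and exact 95% Clopper-Pearson CI of subjects reporting an event". For Tables 154–158 it says only "The total number of laboratory confirmed ZIKV or DENV infections are summarized by treatment group, baseline flavivirus status, and confirmation method in" those tables, and names no interval.

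**The concern.** A Clopper-Pearson interval has its stated level when the count is binomial, that is, a sum of independent trials with a common probability. If one subject contributes two or more illnesses and their status tends to agree, the effective number of observations is below the number of events, and the interval claims more precision than the data hold.

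Tables 154–160 are where the plan puts intervals on the share of illnesses that are confirmed, and on confirmation crossed with medication use or medical care, by treatment group. Placebo has about 10 subjects in all and the ZPIV groups about 35 and 45, so event counts may be small and a few subjects could dominate a cell.

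**Working it through.** **Is there a reason in the documents to expect correlation?** For one confirmation route, yes. SAP sections 3.3 and 4.5 compare neutralization titers in the samples immediately before and after the illness visit. Section 4.5 schedules humoral samples on Days 1, 15, 29, 43, 57, 209 and 388 within the period these tables cover. Two illnesses in one subject between the same two sampling days use the same pair of samples and must get the same titer-rise result.

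To gauge how often, assume illness days uniform over Days 1–388. The gaps are 14, 14, 14, 14, 152 and 179 days (total 387). The chance that two illnesses share a gap is (4×14² + 152² + 179²)/387² = 55,929/149,769 ≈ 37%. From Day 57 on it is (152² + 179²)/331² = 55,145/109,561 ≈ 50%. This affects the titer-rise rows directly and the any-positive and negative rows in part. The documents give no correlation for PCR status, medication or medical care.

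**Effect on width.** Table 154 is an empty shell, so there is no plan figure to reproduce. Assume 20 events with 20% confirmed. The planned interval for 4/20 is 5.7–43.7%, width 37.9 points. With mᵢ events in subject i and within-subject correlation ρ, deff = 1 + ρ(Σmᵢ²/Σmᵢ − 1) and n_eff = 20/deff, and Clopper-Pearson is then applied at n_eff.

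- 15 subjects, five with two events: Σmᵢ² = 10×1 + 5×4 = 30, so deff = 1 + 0.5ρ. At ρ = 0.5, n_eff = 16.0 and the interval is 4.6–47.0% (width 42.4).
- 10 subjects with two events each: Σmᵢ² = 40, so deff = 1 + ρ. At ρ = 1, n_eff = 10 and the interval is 2.5–55.6% (width 53.1).
- ρ = 0: no change in either pattern.

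**Coverage of the planned event-level interval.** Assumed: 20 events; true shares 10%, 20%, 30% and 50%; a common-shock model for correlation; 200,000 simulated trials per setting.

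| Pattern | ρ = 0 | ρ = 0.3 | ρ = 0.5 | ρ = 1 |
|---|---|---|---|---|
| 19 subjects, one with two events | 95.9–98.9% | 95.5–98.8% | 95.4–98.7% | 94.8–98.4% |
| 15 subjects, five with two events | 95.8–98.9% | 94.2–98.2% | 93.0–97.8% | 90.0–96.8% |
| 10 subjects, two events each | 95.8–98.9% | 92.5–97.6% | 90.0–96.8% | 86.0–92.9% |
| 5 subjects, four events each | 95.9–98.9% | 85.3–94.9% | 78.5–93.1% | 61.4–91.9% |

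One cell can be checked by hand. With 10 subjects, two events each, ρ = 1 and true share 20%, the event count is twice a Binomial(10, 0.2) variable. Zero events gives an upper limit of 1 − 0.025^(1/20) = 16.8%, which misses 20%. Eight gives a lower limit of 19.1%, which includes it. Ten gives 27.2%, which misses. Coverage is P(1 to 4 positive subjects) = 0.2684 + 0.3020 + 0.2013 + 0.0881 = 0.8598, or 86.0%.

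**Opposite sign.** If each pair of illnesses can contain at most one confirmed event (10 pairs, true share 10–30%), coverage is 99.2–99.8%, so the interval is too wide.

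**Variable event numbers.** With one plus a Poisson number of events per subject, beta-binomial status, true share 0.4 and intraclass correlation 0.5, coverage is about 92% (20 subjects, mean 1.5 events), 90% (10 or 20 subjects, mean 2) and 83–84% (10 subjects, mean 3). At intraclass correlation 0.1 the same settings give 95.9%, 95.2–95.7% and 94.3%.

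**The case against.** A reader might infer that these intervals are too narrow whenever a subject has more than one illness. The documents do not support that. Clopper-Pearson is conservative at these sample sizes and absorbs a single repeat or a weak correlation. At zero correlation the interval is valid despite repeats, and at negative correlation it is too wide. Outside the shared titer pairs, neither the sign nor the size of the correlation is given. The Table 161 rule is a contingency for repeats, not a forecast of them. An average of three illnesses per affected subject, which the 83–84% figure needs, has no basis in the plan. All of this stands.

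It can also be said that the plan already has subject-level intervals. Tables 140–146 cover medication and medical care, and Tables 147–153 cover the same confirmation categories. The first exploratory endpoint is itself a proportion of subjects. This stands too, but those tables divide by the whole Safety population and do not cross confirmation with medication or care, so they do not replace the share of illnesses in Tables 154–160. Printing subject counts beside event counts helps a reader see repeats but does not correct the interval.

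Finally, changing the unit to subjects changes the quantity. Suppose 10 subjects have two events each, and 8 positive events fall in 7 subjects. The event share is 8/20 = 40% (19.1–63.9%) and the subject share is 7/10 = 70% (34.8–93.3%). A per-subject figure is therefore a different summary, not a corrected interval for the same one.

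**Conclusion.** The point holds in conditional form. Tables 154–160 treat repeat illnesses as independent trials, and nothing in the SAP secures the 95% level. Under-coverage needs both a material share of repeats and positive within-subject correlation. The titer-rise rule supplies one mechanism for that correlation; the rest is unknown. With 20 assumed events the loss runs from negligible (one repeat) to roughly 2–9 points below nominal (10 subjects with two events each, full correlation). Heavier clustering would cost more. These sizes rest on assumed event counts, repeat patterns and correlations.

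The consequence is small. The endpoint is exploratory, protocol section 11.1 disclaims formal hypothesis testing, and no decision is tied to these intervals. A conclusion that the surveillance results lack valid intervals altogether would go too far, given Tables 140–153.

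**What to change.** In Tables 154–160, keep the event counts and the percentage of events, and either remove the Clopper-Pearson interval or replace it with one that accounts for clustering by subject. State the choice in the footnote and in section 9.9, which at present names no interval for Tables 154–158.

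If an exact interval is wanted, add a separately labelled subject-level proportion: subjects with at least one event in the category, divided by subjects with at least one AFI/ARI. The footnote should say that this is not the share of events, and that a subject with both a positive and a negative illness counts in both rows.

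The cost is a footnote and shell edit, with no new data. The tables would have one fewer column, or slightly wider intervals if the correlation is positive.
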